#### 13.2. Assessing Adverse Events

In conjunction with the medical monitor, the Investigator will evaluate adverse events to ensure the events are categorized correctly. Elements of categorization will include:

- Seriousness/Classifications (see definition in Section 13.1)
- Causality or Relatedness i.e. the relationship between the test article, study treatment or study procedures and the adverse event (not related; unlikely related; possibly related; related see definition in Section 13.2.1)
- Adverse Event Severity Adverse event severity is used to assess the degree of intensity of the adverse event (mild; moderate; severe for all events see definition in Section 13.2.2).
- Outcome not recovered or not resolved, recovering or resolving, recovered or resolved with sequelae, recovered or resolved, death related to adverse event, or unknown.

• Actions Taken – none; temporarily discontinued; permanently discontinued; other

#### 13.2.1. Causality Assessment

**Causality** Assessment – A determination of the relationship between an adverse event and the test article. The test article relationship for each adverse event should be determined by the investigator using these explanations:

- Not Related- An adverse event that is not related to the use of the test article, study treatment or study procedures.
- Unlikely Related An adverse event for which an alternative explanation is more likely, e.g. concomitant treatment, concomitant disease(s), or the relationship of time suggests that a causal relationship is not likely.
- Possibly Related An adverse event that might be due to the use of the test article, or to the study treatment or study procedures. An alternative explanation, e.g. concomitant treatment, concomitant disease(s), is inconclusive. The relationship in time is reasonable. Therefore, the causal relationship cannot be excluded.
- Related An adverse event that is listed as a possible adverse effect (device) or adverse reaction (drug) and cannot be reasonably explained by an alternative explanation, e.g. concomitant treatment of concomitant disease(s). The relationship in time is very suggestive, e.g. it is confirmed by de-challenge and re-challenge.

#### 13.2.2. Severity Assessment

**Severity Assessment** – A qualitative assessment of the degree of intensity of an adverse event as determined by the Investigator or reported to him/her by the subject. The assessment of severity is made irrespective of test article, study treatment or study procedure relationship or seriousness of the event and should be evaluated according to the following scale:

- Mild Event is noticeable to the subject, but is easily tolerated and does not interfere with the subject's daily activities
- Moderate Event is bothersome, possible requiring additional therapy, and may interfere with the subject's daily activities
- Severe Event is intolerable, necessitates additional therapy or alteration of therapy and interferes with the subject's daily activities

#### **13.3. Documentation and Follow-Up of Adverse Events**

The recording and documenting of adverse events (ocular and non-ocular) begins when the subjects are exposed to the test article, study treatment or study procedure. Adverse events reported before the use of test article, start of study treatment, or study procedures will be recorded as medical history. However, if the condition deteriorates at any time during the study it will be recorded and reported as an AE. Untoward medical events reported after the subject's exit from the study will be recorded as adverse events at the discretion of the Investigator.

Upon finding an adverse event, the Principal Investigator will document the condition in the subject record and in the eCRFs. He/she will complete the Adverse Event /eCRF.

Complete descriptions of all adverse events must be available in the subject record. All Adverse Events including local and systemic reactions not meeting the criteria for "serious adverse events" shall be captured on the appropriate case report form or electronic data system. All adverse events occurring while the subject is enrolled in the study must be documented appropriately regardless of relationship.

It is the Investigator's responsibility to maintain documentation of each reported adverse event. All adverse events will be followed in accordance with applicable licensing requirements. Such documentation will include the following:

- Adverse event (diagnosis not symptom)
- Drawings or photographs (where appropriate) that detail the finding (e.g., size, location, and depth, etc.)
- Date the clinical site was notified
- Date and time of onset
- Date and time of resolution
- Adverse event classification, severity, and relationship to test articles, as applicable
- Treatment regimen instituted, including concomitant medications prescribed, in accordance with applicable licensing requirements
- Any referral to another health care provider if needed
- Outcome, ocular damage (if any)
- Likely etiology
- Best corrected visual acuity at the discovery of the event and upon conclusion of the event

In addition, if an infiltrate(s) is present, he/she will complete the Corneal Infiltrate Assessment eCRF **Cornection**. Where necessary, a culture of the corneal lesion will be collected to determine if the infection is microbial in nature. If cultures are collected, the date of culture collection and laboratory utilized will be recorded.

Changes in the severity of an AE shall be documented to allow an assessment of the duration of the event at each level of intensity to be performed. Adverse events characterized as intermittent require documentation of the onset and duration of each episode. Changes in the assessment of relationship to the Test Article shall also be clearly documented.

Subjects who present with an adverse event shall be followed by the Investigator, within licensure, until all signs and symptoms have returned to pre-treatment status, stabilized, or been satisfactorily resolved. If further treatment beyond licensure is required, the patient will be referred to the appropriate health care provider. The Investigator will use his/her clinical judgment as to whether or not a subject reporting with an adverse event will continue in the study. If a subject is discontinued from the study, it will be the responsibility of the Investigator to record the reason for discontinuation. The Investigator will also document the adverse event appropriately and complete the Adverse Event eCRF. Any subjects with ongoing adverse events related to the test article, study treatment or study procedures, as of the final study visit date, should be followed to resolution of the adverse event or until referral to an appropriate health care provider. Non-ocular adverse events that are

not related to the test article, study treatment, or study procedures may be recorded as "ongoing" without further follow-up.

#### 13.4. Reporting Adverse Events

The Investigator will notify the Sponsor of an adverse event by e-mail, facsimile, or telephone as soon as possible and no later than 24 hours from discovery for any serious /significant adverse events, and 2 days from discovery for any non-significant adverse event. In addition, a written report will be submitted by the Principal Investigator to the IEC/IRB according to their requirements (Section 13.4.2). The report will comment whether or not the adverse event was considered to be related to the test article, study treatment or study procedures.

#### 13.4.1. Reporting Adverse Events to Sponsor

#### Serious/Significant Adverse Events

The Investigator will inform the sponsor of all serious/significant adverse events occurring during the study period as soon as possible by e-mail, fax, or telephone, but no later than 24 hours following discovery of the event. The Investigator is obligated to pursue and obtain information requested by the Sponsor in addition to that information reported on the eCRF. All subjects experiencing a serious/significant adverse event must be followed up and all outcomes must be reported.

When medically necessary, the Investigator may break the randomization code to determine the identity of the treatment that the subject received. The Sponsor and study monitor should be notified prior to unmasking the test articles.

In the event of a serious/significant adverse event, the Investigator must:

- Notify the Sponsor immediately
- Obtain and maintain in the subject's records all pertinent medical information and medical judgment for colleagues who assisted in the treatment and follow-up of the subject
- Provide the Sponsor with a complete case history which includes a statement as to whether the event was or was not related to the use of the test article
- Notify the IEC/IRB as required by the IEC/IRB reporting procedure according to national regulations

#### Unanticipated (Serious) Adverse Device Effect (UADE)

In the event of an Unanticipated (Serious) Adverse Device Effect (UADE), the Investigator will submit a report of the UADE to the Sponsor and IEC/IRB as soon as possible, but no later than 24 hours after the Investigator first learns of the effect. This report is in addition to the immediate notification mentioned above.

The Sponsor must conduct an evaluation of the UADE and must report the results of the evaluation to FDA, the IEC/IRB and participating Investigators within 10 working days after the Sponsor first receives notification of the effect.

#### Non-Serious Adverse Events

All non-serious adverse events, including non-serious adverse device effects, will be reported to the sponsor by the Investigator no later than 2 days from discovery.

#### 13.4.2. Reporting Adverse Events to the Responsible IEC/IRB and Health Authorities

Adverse events that meet the IEC/IRB requirements for reporting must be reported within the IEC/IRB's written guidelines. Each clinical site will refer to and follow any guidelines set forth by their Approving IEC/IRB. Each clinical site will refer to and follow any guidelines set forth by their local governing Health Authorities.

The Sponsor will report applicable Adverse Events to the local health authorities according the written guidelines, including reporting timelines.

#### 13.5. Event of Special Interest

# 13.5.1. Specific Requirements for Recording and Diagnosing Possible Microbial Keratitis

The signs of a presumed infectious ulcer (defined as progressive erosion of the corneal tissue) may include irregular focal infiltrates (>1 mm); active lesions with raised edges; significant diffuse infiltration; anterior corneal to mid-stromal involvement; erosion with overlying staining; conjunctival and lid edema; anterior chamber reaction (iritis); severe bulbar and limbal redness. Symptoms associated with a presumed infectious ulcer (microbial keratitis, MK) may include pain of rapid onset; severe redness; purulent or mucopurulent discharge; tearing; photophobia. For the purpose of reporting, per the ISO 11980, a presumed corneal ulcer which has any of the following characteristics should be reported as a serious adverse event:

- 1. Central (6 mm) or paracentral (8 mm) location;
- 2. Penetration of Bowman's membrane;
- 3. Infiltrate> 2mm diameter
- 4. Associated with iritis  $\geq$  Grade 2;
- 5. Associated with any increase in intraocular pressure;
- 6. Culture positive for microorganisms;
- 7. Increasing size of severity at subsequent visits.

In the event of any case of possible microbial keratitis (e.g., presence of an infiltrative lesion), the investigators shall provide complete descriptions of the event. A comprehensive description of diagnostic procedures is provided

The investigator shall record the following in the CRF:

- Presence and severity of pain;
- Presence and type of discharge;
- Presence of lid edema;
- Presence of chemosis;
- Pattern and grading of redness (bulbar/limbal);

- Characterization of infiltrates (size, shape, location, depth) on the Infiltrate Assessment Form;
- Characterization of the epithelial defect (size/depth);
- Involvement of surrounding cornea;
- Endothelial involvement;
- Grading of anterior chamber cell and flare

The investigator shall record the diagnosis and specific treatment on the Adverse Event Form.

Where necessary, a culture of the corneal lesion will be collected to determine if the infection is microbial in nature. For example, if an overlying epithelial defect is present and any one of the conditions listed below is present when the infiltrate is first evaluated, the infiltrate must be cultured.

- Diameter greater than 1mm
- Location within the central (6 mm) optical zone
- Purulent discharge
- Pain
- Photophobia
- Iris/Anterior chamber inflammation

Any corneal lesions meeting the criteria set forth above must be cultured as outlined in the Premarket Notification (510(k)) Guidance Document for Daily Wear Contact Lenses (Revised May 1994). Cultures will be collected with the Sponsor approved culture kits and sent to a study designated laboratory for analysis. The results will be communicated to the Investigator and the Sponsor. See for specific procedures that should be followed for culturing of possible cases of infectious keratitis.

For other infiltrative events that do not meet the criteria as specified above, the investigators may culture the lesion when deemed appropriate. If cultures are collected, a source document note should be completed specifying the date of culture collection and laboratory utilized. An eCRF documenting this should be completed.

All cases of symptomatic corneal infiltrates shall be reported to DMC. The DMC will serve as an independent committee to adjudicate whether the event should be classified as infectious or non-infectious by majority vote. The following definitions will be used to classify whether the case is definite MK, probable MK, probably not MK, definitely not MK, or MK unrelated to contact lens wear. 

- **Definite MK**: one or more central (6 mm) or paracentral (8 mm) corneal stromal infiltrates greater than 2mm in size with pain rated more than mild, and one of the following:
  - o anterior chamber reaction (iritis) Grade 2 or higher
  - mucopurulent discharge
  - positive corneal culture

- **Probable MK**: same definition as that of definite MK but failing to meet all of the specified criteria, e.g., the size of the lesion was less than 2mm, the pain was minimal, or there was less than Grade 2 anterior chamber reaction, no mucopurulent discharge, or negative corneal culture.
- **Probably not MK**: not meeting any of the above specified MK definitions.
- **Definitely not MK**: not meeting any of the above specified MK definitions and with significant evidence that suggests non-infectious etiology (e.g. reduction in severity without pharmacologic treatment).
- **MK unrelated to contact lens wear**: cases such as *Herpes simplex* keratitis or *Staphylococcal* marginal keratitis, where, in the judgment of the panel, the etiology is unrelated to the wear of contact lenses.

#### 13.5.2. Loss of Best Sphero-cylindrical Corrected Visual Acuity without Physical Cause

During the course of the study, if it is found that best sphero-cylindrical corrected visual acuity (BSCVA) of a subject is less than 20/25 (0.1 logMAR) in either eye and is more than 1.5 lines worse than that was measured at baseline without any physical cause (confirmed through up to 3 repeated independent measures to rule out potential measurement errors or variations), the subject will cease wearing the study lenses and an adverse event will be filed. The subject will be followed until the best corrected visual acuity is no more than 1.5 lines worse than baseline or is stabilized before being discontinued from the study. A decrease of more than 1.5 lines of BSCVA is considered a significant change. This criterion is established based on the 95% limits of agreement of repeated measures of visual acuity in children. 

It is not anticipated that development of amblyopia (defined as a reduction of BSCVA to 20/30 or worse or a two-line difference between the two eyes, in the absence of pathology ) will occur while wearing the investigational soft contact lens. Upon identifying the first confirmed case of amblyopia during the course of the study, the event will be investigated and followed according to procedures specified for an Unanticipated Adverse Device Effect (Sections 11 and 13.1).

#### **13.6.** Reporting of Pregnancy

Subjects reporting pregnancy (by self-report) during the course of the study will be discontinued after the event is recorded as an Adverse Event. Once discontinued, pregnant participants and their fetuses will not be monitored for study related purposes. At the Investigator's discretion, the study participant may be followed by the Investigator through delivery. However, this data will not be collected as part of the clinical study database. Pregnant participants are not discontinued from contact lens or solution related studies for safety concerns, but due to general concerns relating to pregnancy and contact lens use. Specifically, pregnant women are discontinued due to fluctuations in refractive error and/or visual acuity that occur secondary to systemic hormonal changes, and not due to unforeseen health risks to the mother or fetus.

#### **14. STATISTICAL METHODS**

#### 14.1. General Considerations

Statistical Analysis will be undertaken by the Sponsor. A general description of the statistical methods to be implemented in this clinical trial is outlined below.

All data summaries and statistical analyses will be performed using the SAS software Version 9.4 (SAS Institute, Cary, NC). Throughout the analysis of data, the results for each subject/eye will be used when available for summarization and statistical analysis. Unscheduled visits will be summarized separately and will be excluded from the statistical analysis.

Summary tables (descriptive statistics and/or frequency tables) will be provided for all baseline variables, efficacy variables and safety variables as appropriate. Continuous variables will be summarized with descriptive statistics (n, mean, standard deviation (SD), median, minimum and maximum). Frequency count and percentage of subjects or eyes within each category will be provided for categorical data.

All statistical analysis will be conducted on the per-protocol population defined in section 14.3.

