#### 14.3. Analysis Populations

#### **Safety Population:**

All subjects who are administered any test article excluding subjects who drop out prior to administering any test article. At least one observation should be recorded.

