#### **Per-Protocol Population:**

All subjects who have successfully completed the initial screening and baseline visit (Visit 1), the study lens fitting and dispensing visit (Visit 2), and the 6-month follow up visit (Visit 6), and did not substantially deviate from the protocol as determined by the trial cohort review committee prior to database hard lock (Per-Protocol Population). Justification of excluding subjects with protocol deviations in the per-protocol population set will be documented in a memo to file.

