#### Intent-to-Treat (ITT) Population:

All randomized subjects regardless of actual treatment and subsequent withdrawal from study or deviation from protocol. At least one observation should be recorded.

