#### 14.5. Primary Analysis

The two primary endpoints, changes of axial length (AL) and cycloplegic auto refraction (SECAR) from baseline at 6 months follow-up, will be analyzed separately using a linear mixed model for longitudinal data. Each model will include treatment group, time period (in weeks) and treatment group by time interaction as fixed effect factors; and site, subject nested in site, and eye nested in subject as random effect factors when appropriate. Other baseline characteristics known of importance such as age, gender, refractive error at baseline, axial length at baseline, pupil size, parental history of myopia and other factors will be included as fixed covariates when appropriate. The covariance between residual errors from the same subject/eye across lens wearing time periods will be selected based on the finite-sample corrected Akaike's Information Criterion. Covariance structures considered may include: Homogeneous Compound Symmetry (CS), first-order autoregressive (AR(1)) and Unstructured covariance structure (UN). For AR (1) structure, site, subject nested in site and eye nested in subject will be included in each model as random effects. For the remaining structures, only site and subject will be included as random effects. The covariance structure that returns the lowest Akaike Information Criteria Corrected (AICC) will be selected as the structure that best fit the data. Heterogeneous residuals covariance structures (R-side) across treatment groups will be considered when appropriate. The log-likelihood ratio test will be

used to test for the homogeneity between the residual covariance structures. The Kenward and Roger method will be used for the denominator degree of freedom.

The null and alternative hypotheses for superiority for each test lens relative to the control are as follows for AL and SECAR:

$$H_0: \Delta_{AL} \ge 0; H_A: \Delta_{AL} < 0;$$
$$H_0: \Delta_{SECAR} \ge 0; H_A: \Delta_{SECAR} < 0,$$

where  $\Delta_{AL}$  and  $\Delta_{SECAR}$  are the mean differences (Test minus Control) in change from baseline of AL and SECAR at 6 months follow-up respectively.

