#### 14.9. Procedure for Handling Missing Data and Drop-Outs

Missing or spurious values will not be imputed. The count of missing values will be included in the summary tables and listings.

Subject dropout is expected to be one of the main reasons of missing data in this clinical trial. Past clinical trials don't provide the evidence that subject dropout is systematic or not-at-random. To evaluate the impact of missing data, sensitivity analysis will be conducted using multiple imputation methods if the proportion of subject dropout is greater than the 15%. The SAS/STAT procedures PROC MI and PROC MIANALYZE will be utilized with a parametric regression method used to make at least 50 imputations.

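### The AL and SECAR superiority tests rest on per-protocol completers only; the ITT set is defined but used in no analysis

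*Combined protocol and SAP*

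**What the plan says.** Section 14.1 sets one population for everything: "All statistical analysis will be conducted on the per-protocol population defined in section 14.3". Section 14.5, which holds the mixed models and the superiority rule, names no other.

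Under 14.3, a per-protocol child must have completed Visits 1 and 2 "and the 6-month follow up visit (Visit 6), and did not substantially deviate from the protocol", the last condition "as determined by the trial cohort review committee prior to database hard lock". The same section defines ITT as "All randomized subjects regardless of actual treatment and subsequent withdrawal from study or deviation from protocol". Apart from the abbreviation list, ITT appears nowhere else.

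On missing data, 14.9 says "Missing or spurious values will not be imputed", and then that "sensitivity analysis will be conducted using multiple imputation methods if the proportion of subject dropout is greater than the 15" per cent. It names no population for that analysis and does not say whether dropout is counted per arm or pooled.

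Section 14.5 also allows some baseline adjustment: "parental history of myopia and other factors will be included as fixed covariates when appropriate". Section 2.3 requires a Test lens to succeed on both AL and SECAR, and 14.4 sets an overall 5% error rate.

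**The concern.** Several exits after lens assignment may depend on the lens. At dispensing (step 2.18) and again at follow-up (step 3.16), a child must reach set acuity limits with the study lens on and find its vision acceptable. Section 8.2 adds low wear time, poor comfort and unacceptable fit. Section 1 warns that the added plus power may harm vision, whereas the Control lens is single-vision (4.2). Unequal loss between Test and Control is therefore foreseeable, although Section 1 also reports satisfactory pilot results for EMO-114 and EMO-118.

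If losses differ by arm and are related to progression, the completers no longer form the groups that were randomised. At stake are the formal superiority claims and, because 14.2 says the data will inform later trials, the effect estimates carried forward. Under 5.3 and 8.2 discontinued children may be replaced during enrolment, so reaching 40 per arm would not show that selection was absent.

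**Working it through.** **1. Who is lost, and what data they have.**

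- A child never dispensed a lens has baseline data only.
- A child leaving between Visits 3 and 5 has AL from one or more of those visits (step 3.12). Section 8.2 requires the current visit to be completed, and AL comes before the continuance check at 3.16. There is no post-baseline SECAR, because Table 3 next schedules cycloplegic refraction at Visit 6. The Final Evaluation measures neither endpoint.
- A child withdrawn at Visit 6 should have both endpoints, because steps 6.26 to 6.30 come before the check at 6.34.

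The per-protocol set drops the first two groups entirely. It also drops any child with a completed Visit 6 who is judged to have deviated substantially.

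**2. The imputation.** Read with 14.1, the 14.9 analysis would run on a set that contains no one who left before Visit 6. The trigger can also miss unequal loss. Assume equal arms, all exclusions counted as dropouts, and pooling over arms:

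- Three Test arms losing 15% and Control 10%: (3 × 15 + 10)/4 = 13.75%.
- One Test arm losing 30% and the other three arms 10%: (30 + 3 × 10)/4 = 15.0%.

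Neither exceeds 15%, so no imputation would run.

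**3. The plan's own figures.** Section 14.2 uses 40 per arm, SD 0.10 mm (AL) and 0.32 D (SECAR), two-sided 0.05. A two-sample t-test gives AL power 0.598, 0.942, 0.993 and 0.9996 (stated 0.60, 0.94, 0.99, 0.99) and SECAR power 0.544, 0.788 and 0.932 (stated 0.54, 0.79, 0.93). The SECAR 0.10 D row (stated 0.03, computed 0.28) does not reproduce; that is a separate matter. The plan gives no figure for loss after randomisation.

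**4. Illustration of bias.** All inputs here are assumptions except the 40 per arm and the SDs. Let f be the fraction excluded and g the gap in mean progression, excluded minus retained, in SD units. With no true effect, the retained mean in an arm is shifted by −f × g, so the apparent Test benefit is (fT − fC) × g. The noncentrality is (fT − fC) × g / √(2/40), with √(2/40) = 0.2236, 78 degrees of freedom and critical t 1.991. Both endpoints must pass, so the joint favourable rate was simulated for AL–SECAR correlations of 0.4 to 0.8 and g of 0.5 to 1 SD on both endpoints. Setting fC = 0 stands for Control exclusions unrelated to outcome.

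| Case | Shift, AL (mm) | Shift, SECAR (D) | Joint rate per lens |
|---|---|---|---|
| No bias | 0 | 0 | 0.3–1.1% |
| Test 15%, Control 10% | 0.0025–0.005 | 0.008–0.016 | 0.5–1.9% |
| Test 15%, Control unrelated | 0.0075–0.015 | 0.024–0.048 | 1.0–5.4% |
| Test 10%, Control 15% | against Test | against Test | 0.15–0.80% |

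Shifts are (fT − fC) × g × SD; for example, 0.15 × 1 × 0.10 = 0.015 mm. If covariates explained half the gap, the second and third rows would fall to 0.4–1.5% and 0.6–2.6%.

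Against the smallest planning differences, the third row is 0.0075/0.05 to 0.015/0.05 = 15–30% for AL, and 0.024/0.10 to 0.048/0.10 = 24–48% for SECAR.

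**The case against.** The strongest reply is that this is a self-described pilot and proof of concept (14.2, 4.2), for which an effect among children who actually wore the lens is a fair aim. That supports keeping per-protocol as a supportive analysis. It does not support using it alone for formal superiority claims.

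The plan has safeguards. Exclusions are settled before hard lock and justified in a memo, and the mask normally holds until the database is final (5.3). Covariates may absorb part of any selection, and both endpoints must pass. These limit arm-aware exclusion and lower the false-positive rate, but they do not address lens-driven dropout.

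It can also be said that an imputation meant to gauge dropout only makes sense on a set that contains dropouts, so 14.9 lacks wording rather than a plan. That is a reasonable guess at intent, but 14.1 read literally says otherwise. The 15.0% example was chosen to fall on the boundary and depends on pooling.

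Three stronger readings should not be drawn:

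- A reader might infer that unequal loss would go unseen. Section 14.7 always summarises disposition, reasons for discontinuation and deviations. These would show it, though not correct for it.
- A reader might infer that adverse events of children who leave would be lost. Section 14.6 specifically uses all available data from the whole study for serious and significant ocular events.
- A reader might take the gap between 240 enrolled and 160 completing as planned dropout. Enrolment is counted from consent (4.3), so the gap includes losses before randomisation.

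**Conclusion.** The point holds and should be fixed. On the text it is certain: the primary tests use a set selected after lens assignment, ITT is unused, and the only planned correction is conditional and has no stated population.

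The size is uncertain. A reader might infer that the design favours the Test lenses or breaches the 5% level. The documents do not support either. They do not link lens-on vision or wear time to progression, so the direction cannot be derived, and in the reversed case the bias works against the Test lens. In the illustration, only the corner with a 1 SD gap on both endpoints, Control exclusions unrelated to outcome and correlation 0.8 exceeds 5%, at 5.4%. All rates are per lens; multiplicity over three lenses is a separate question.

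**What to change.** **14.1 and 14.5:** make ITT (all randomised, as assigned) the primary population for AL and SECAR, with per-protocol supportive. State in 14.3 that a baseline measurement satisfies the one-observation condition in the ITT definition. Fit the planned mixed model to all available data, including AL at Visits 3 to 5 from children who later leave and both endpoints from every child measured at Visit 6.

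**14.9:** drop the 15% trigger. Run the planned multiple imputation on ITT in every case as a sensitivity analysis, with arm, baseline covariates and available AL in the imputation model. Add one delta-adjusted or control-based scenario. It is best not to apply the claim rule to the imputed estimate, because missing-at-random imputation credits never-dispensed children with a lens they did not wear.

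**Cost:** SAP wording and programming; PROC MI with at least 50 imputations is already planned, and no visit or procedure changes. The effect may be diluted. For example, assume 15% dropout with no lens effect, 47 randomised per arm to give 40 completers, and all 47 analysed with the same SD. An AL effect of 0.08 mm becomes 0.85 × 0.08 = 0.068 mm (power 0.90 against 0.94), and a SECAR effect of 0.20 D becomes 0.85 × 0.20 = 0.17 D (0.72 against 0.79). For children who leave before Visit 6, SECAR will rest on missing at random, so some bias may remain; the added scenario is there to show how much that matters.
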